14.3 Secondary objectives

One of our secondary exploratory objectives is to estimate the uptake in tumors. We will present lesion-based summary statistics for the uptake adjusted for clustering. Another secondary objective is to correlate ⁸⁹Zr-DFO-MSTP2109A imaging to response to treatment in those patients recruited to protocol 11-016 DSTP3086S ADC. Outcome measures to be correlated include those that are outlined in the parent protocol 11-016 and include PSA response, RECIST response, presence or absence of new bone scan lesion and progression free survival. We will use Kaplan-Meier estimates and 95% confidence intervals to correlate these outcomes with imaging response.

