1.0 PROTOCOL SUMMARY AND/OR SCHEMA

Summary

Metastatic prostate cancer is predominantly bone-tropic, and bone metastases result in blood dyscrasias, cord compression, fracture, pain, neurologic compromise, and death. New therapies are desperately needed, and many novel targeted therapies, androgen receptor (AR)-targeted treatments, chemotherapies, vaccines, immunologic drugs and immunotoxins are currently being tested. Unfortunately, drug development and clinical care for these patients is significantly hampered by the lack of any standard means of accurately assessing the primary reservoir of distant disease, which is embedded in the marrow of the axial skeleton.

Bone scintigraphy demonstrates reactive bone deposition only and not the cancer itself. Bone lesions shown on computerized tomography (CT) and plain radiographs generally only appear as sclerotic lesions that bear no relation to active tumor size, nor can these methods distinguish between the healing effects of successful therapy vs. the osteoblastic response of bone to a tumor that is continuing to progress on therapy.

The lack of good imaging methods hampers decision making in terms of when to apply or modify conventional treatment methods as well as limiting new drug development. Accurate imaging modalities are particularly needed in the age of targeted or biologic therapies, where effective therapies may be cytostatic and may not result in significant prostate-specific antigen (PSA) declines. In such cases, molecular imaging may be the only means by which early biologic activity of a new drug may be detectable in a Phase I or Phase II study. Furthermore when targeted therapies are to be used it is desirable to have an imaging test that identifies that the target is present in order to select patients and that may be also be used to determine if the target is being "hit" or downregulated. Many examples of this target selection and monitoring approach exist. Examples include bone scan for selection of radionuclide therapy with Sm-153 EDTMP or Sr-89 chloride, I-123 MIBG to select patients for I-131 MIBG therapy or In-111/Ga-68 Somatostatin receptor scintigraphy to select patients for Y-90/Lu-177 Somatostatin receptor therapy.

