2.2 Secondary Objectives

- To determine the better/"adequate" ⁸⁹Zr-DFO-MSTP2109A mass amount for tumor imaging (10 or 20 mg) .
- To determine optimal time relative to ⁸⁹Zr-DFO-MSTP2109A administration for tumor imaging.
- To use quantitative biodistribution data of ⁸⁹Zr-DFO-MSTP2109A uptake to perform dosimetry estimates.
- To correlate ⁸⁹Zr-DFO-MSTP2109A uptake in tumors with STEAP1 antigen expression by IHC
- To explore whether ⁸⁹Zr-DFO-MSTP2109A PET imaging results are related to patient outcome in patients being treated with DSTP3086S.

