6.1 CRITERIA FOR SUBJECT ELIGIBILITY

6.2 Subject Inclusion Criteria

To be included in this study, patients should be eligible for enrollment into protocol 11-016 (therapy with the DSTP3086S ADC) or meet all of the following criteria:

- Patients meeting the criteria for enrollment on research protocol 11-016 to receive

MEMORIAL SLOAN-KETTERING CANCER CENTER IRB PROTOCOL

IRB#:12-178 A(3)

DSTP3086S ADC (therapeutic ADC based on MSTP2109A) will be the preferred patients for this study. Patients that are to receive DSTP3086S will not be injected with DSTP2086S until imaging with ⁸⁹Zr-DFO-MSTP2109A is finished, approximately 1 week.

- Adult male >21years of age
- Visible lesions by either CT, bone scan or MRI consistent with metastatic disease
 - Metastatic progressive disease
 - Imaging modalities:
Bone scan: new osseous lesion and/or
MRI or CT: An increase in measurable soft tissue disease or the appearance of new sites of disease.

Or

PSA Changes	Minimum No. of determinations	Interval	Percentage increase over range of values
Androgen independent	3	\geq 1Week	25%
	2	\geq 2Week	

- Patients with histologically confirmed prostate cancer at MSKCC
- STEAP1 antigen positive tissue known from prior IHC testing or if STEAP1 status is not known archival sample will be sent to Genentech for IHC. Samples need to be positive, when feasible metastatic lesions will be tested preferentially rather than the primary.
- Performance status of 60 or higher (Karnofsky scale) (Appendix A)
- Ability to understand and willingness to sign a written informed consent document
- PSA levels to be taken within 2 weeks of antibody administration.

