14.1 BIOSTATISTICS

14.2 Primary Objective

The primary objective of this protocol is to determine the feasibility, safety and tolerability of single dose administration of ^{89}Zr -DFO-MSTP2109A antibody.

A patient with STEAP1 positive tumor will be considered antibody-imaging-positive if 20% or more of the active lesions are detectable (STEAP1 positivity is an eligibility criterion for protocol 11-016 which forms the basis of eligibility for this protocol; see section 6 for details). Active lesion means any lesion that was identified by conventional imaging methods and clinical data at baseline. We have selected a low threshold of 20% for this first imaging study for 3 reasons: 1) we do not know what the heterogeneity of antigen expression is within a number of lesions in the same patient; 2) we will consider positive any lesion based on conventional clinical imaging criteria, in which case some lesions considered positive may be false positive and more importantly 3) our main emphasis is to evaluate whether patients whose tumor images are positive with ^{89}Zr -DFO-MSTP2109A are more likely to have a response to the antibody based drug conjugate used under

MEMORIAL SLOAN-KETTERING CANCER CENTER IRB PROTOCOL

IRB#:12-178 A(3)

protocol 11-016. Thus, we do not want to discard this agent if we can use it as a **theranostic** (defined as an agent that is integrated into the drug development process so as to guide patient selection and drug development) for the development of the antibody base drug conjugate being used under protocol 11-016. Nonethe less, we intend to evaluate treatment response of all available lesions in this way we will maximize our ability to determine the relationship between uptake of antibody and response.

If, for any patient, there is evidence of an “antigen sink” based on rapid clearance < 50 h or $Vd > 3$ times plasma volume, we will consider a patient antibody-imaging-positive if 20% or more of the active lesions are visualized. The presence of an “antigen sink” may bind a significant amount of antibody and make less available for binding to tumor.

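### The exploratory analysis of imaging against conjugate outcome names PSA and RECIST response but no percent change, which costs precision in at most 27 men

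*Combined protocol and SAP*

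**What the plan says.** Section 2.2 sets the aim: "To explore whether ⁸⁹Zr-DFO-MSTP2109A PET imaging results are related to patient outcome" among men treated with the conjugate. Section 14.3 restricts the analysis to imaged men "in those patients recruited to protocol 11-016 DSTP3086S ADC" and takes its endpoints from that trial: "Outcome measures to be correlated include those that are outlined in the parent protocol 11-016". The named endpoints "include PSA response, RECIST response, presence or absence of new bone scan lesion and progression free survival". The only method given is "We will use Kaplan-Meier estimates and 95% confidence intervals to correlate these outcomes with imaging response".

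The section names no percent change in PSA or in lesion size. It gives no response cut-points, assessment time, test, significance level, power or expected number of treated men, and it does not define imaging response.

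Section 14.2 describes whether image-positive patients respond to the conjugate as the main emphasis. It adds an intention to assess response in every available lesion so that "we will maximize our ability to determine the relationship between uptake of antibody and response".

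On the data side, section 6.2 asks for "PSA levels to be taken within 2 weeks of antibody administration", and section 12.0 records SUVmax and SUVmean for lesions identified on the antibody scan.

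**The concern.** As usually defined, a PSA response is a cut applied to percent change in PSA, and a RECIST response is largely a cut applied to percent change in the sum of target lesions. After the cut, a man just short of the threshold counts the same as a man with rapid progression. In a group this small, the discarded information can decide whether an association is visible at all.

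The question at stake is the one the study most wants to inform: whether uptake of the antibody helps to select men for the conjugate. With few responders, the comparison by response status becomes very coarse. Its result could be read as showing no relation when uptake does track the change in PSA.

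**Working it through.** **The plan's own figures.** None is given for this analysis. The figures stated in section 14.2 for the feasibility endpoint reproduce:
- P(3 or fewer of 6) = 0.821 at a true rate of 40% and 0.169 at 75%.
- 1.96 × √(0.75 × 0.25 / 15) = 0.219, the stated 22 points.

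**Number of men.** Cohorts 1A, 1B and 2 give 6 + 6 + 15 = 27, which agrees with the Cohort 2 schedule footnote on the 13th to 27th patients. Without cohort 1B it is 6 + 15 = 21. Section 4.3 lets men enrol who are not considered for the conjugate, so the treated number may be lower. It is not stated.

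**Why a cut loses information.** Assume that uptake and percent change are bivariate normal with correlation ρ, and that a proportion p respond. The correlation of uptake with responder status is ρ × φ(z_p) / √(p(1−p)), where φ(z_p) is the normal density at the cut. The square of that factor approximates the fraction of the sample effectively kept.

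| p | factor | ρ = 0.6 becomes | fraction kept |
|---|---|---|---|
| 15% | 0.233 / 0.357 = 0.653 | 0.39 | 0.43 |
| 30% | 0.348 / 0.458 = 0.759 | 0.46 | 0.58 |
| 50% | 0.399 / 0.500 = 0.798 | 0.48 | 0.64 |

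**Illustrative power.** This is by simulation at two-sided 5%, with continuous uptake. Spearman correlation with percent change is compared with an exact rank-sum of uptake by responder status at ρ = 0.6.

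| n | percent change | response, p = 15% / 30% / 50% |
|---|---|---|
| 15 | 62% | 23% / 37% / 43% |
| 21 | 79% | 35% / 53% / 58% |
| 27 | 90% | 49% / 67% / 73% |

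Repeat runs move these by a point or two, so the ranges quoted are 23-44% at n = 15 and 49-73% at n = 27.

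**Where the gain is small.** At n = 15 and ρ = 0.3, percent change gives about 17%. The gain over response status is about 4-9 points at response rates of 20-50%, and about 10 points at 15%. Both analyses are weak there.

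**If imaging is also kept positive/negative.** With 75% positive, n = 15 and ρ = 0.6, a rank-sum on percent change has about 34% power, against 0-14% for Fisher's exact test on response.

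**Few responders.** With one responder among n men, the smallest two-sided exact rank-sum p-value is 2/n: 0.133 at n = 15 and 0.074 at n = 27. The chance of 0 or 1 responder among 15 is 0.85^15 + 15 × 0.15 × 0.85^14 = 0.087 + 0.231 = 0.32 at a 15% response rate. At 30% it is 0.005 + 0.031 = 0.035.

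**Precision with the better analysis.** For an observed rank correlation of 0.6, an approximate 95% interval is tanh(0.693 ± 1.96 × √(1.06/(n−3))). This gives 0.11 to 0.86 at n = 15 and 0.27 to 0.80 at n = 27. Percent change improves the analysis but does not make it precise.

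**The case against.** The analysis is secondary and exploratory, and no test or power is planned. A reader might infer that a planned power is being lost. The documents do not support that: the rank-sum comparator above is itself an assumption, since section 14.3 names only Kaplan-Meier. This stands, and the power figures are illustrations of lost information. They depend on correlations and response rates that the documents do not give.

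A reader might also infer that with 0 or 1 responder the question could not be answered. That goes too far. The endpoint list is open, it includes progression-free survival and new bone lesions, and section 14.2 adds response at lesion level. The sentence about maximizing ability refers to that lesion-level work, so it is not a promise that section 14.3 breaks.

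A third tempting reading uses the summary's remark that "effective therapies may be cytostatic and may not result in significant prostate-specific antigen (PSA) declines" to predict few PSA responders. That remark concerns targeted and biologic therapies in general, whereas section 3.2.2 describes this conjugate as delivering a cytotoxic payload. If the remark did apply, it would also weaken percent PSA change as an outcome.

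Finally, adopting the parent trial's endpoints is a defensible choice for a companion study. Protocol 11-016 is not among the documents, so its cut-points, number of response categories and assessment times cannot be checked. This argues for keeping the response endpoints. It does not argue against adding the measurements beneath them.

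**Conclusion.** The point holds as a low-cost improvement. Section 14.3 relies on PSA and RECIST response without naming the percent changes behind them, in a group of at most 27 men (21 without cohort 1B, possibly fewer treated). Under the assumptions shown, the gain from percent change is substantial at correlation 0.6 (about 62% against 23-44% for 15 men, 90% against 49-73% for 27) and only a few points at correlation 0.3.

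The cost is less precise estimation, and some risk that an imprecise null result is read as no relation. It is not the loss of a planned power, and the other endpoints remain as routes to the question. That PSA and RECIST response will be analysed as yes/no categories is an inference from their names, because the definitions sit in 11-016.

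One related defect needs no assumption about effect size. Kaplan-Meier estimation is named for all the outcomes, but it does not suit yes/no outcomes without a time to event.

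**What to change.** In section 14.3:

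- Add percent change in PSA from baseline to one fixed 11-016 assessment.
- For men with measurable soft tissue disease, add percent change in the sum of target lesions.
- Relate each to tumor uptake, using one prespecified patient-level summary of lesion SUV, by Spearman correlation with a 95% confidence interval. Alternatively, compare each across imaging status by rank-sum with a 95% confidence interval. State what imaging response means.
- Give the worst rank to men who die or progress before the assessment.
- Keep PSA response and RECIST response as descriptive tables.
- Keep Kaplan-Meier for progression-free survival only.
- State the expected number of men treated on 11-016.

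The cost is SAP wording plus transfer of PSA values and lesion measurements that 11-016 should already hold in order to derive response. No new patient, visit or procedure is needed. There are two small downsides: rank correlations are less familiar to clinicians than response rates, and the lesion-size analysis covers only men with measurable disease.

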4.3 Intervention

The intervention is the administration of a single dose of the ^{89}Zr -DFO-MSTP2109A tracer for imaging purposes. In Cohort 1A or 1B, after administration of the experimental tracer, the patient will undergo up to four PET scans during the 7 days post injection, whole body probe measurements and pharmacokinetics. In Cohort 2, patients will undergo injection of ^{89}Zr -DFO-MSTP2109A, and they will undergo one PET scan from top of skull to mid thigh (this may be adjusted based on known extent of disease) and no pharmacokinetics will be performed. The primary population will be those who are planning to enroll in the therapeutic trial using DSTP3086S (11-016), although for Cohort 1A, 1B and potentially Cohort 2 patients that meet the inclusion criteria may be enrolled even if not considered for DSTP3086S therapy. No clinical management decisions will be made based on ^{89}Zr -DFO- MSTP2109A imaging. Patients may not be re-imaged on this trial.

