Active lesions will be identified (Nuclear Medicine investigator and MM) based on conventional images and those thought to represent active disease based on review of the patients conventional images and treatment history (ie external radiation) will be considered as lesions for determination of antibody localization. A lesion will be considered present if there is greater localization than that expected based on blood pool distribution of the tracer. Given that at present we do not know the heterogeneity of the antigen between lesions or between primary and metastatic disease a patient will be considered positive if any of the active lesions are identified with the ^{89}Zr -DFO-MSTP2109A. We will, nonetheless tabulate the number of lesions and their status based on ^{89}Zr -DFO-MSTP2109A. When pathologic material that has been evaluated for the presence of STEAP1 is available for any specific lesion, we will correlate the presence of STEAP1 with imaging results.

Patients in Cohort 1A (and if performed Cohort 1B) will also have imaging at 4 time points post-injection to allow for selection of optimal imaging time and dosimetry determination. For these patients, top of skull to mid thigh scans will be acquired:

- Within one to four hours following injection of tracer on Day 1
- \sim 24 \pm 8 hours post-injection (Day 2)
- \sim 48–96 hours post-injection (once during Days 3–5)
- \sim 120–168 hours post injection (once during Days 6–8)

MEMORIAL SLOAN-KETTERING CANCER CENTER IRB PROTOCOL

IRB#:12-178 A(3)

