Antibody imaging will be considered feasible if 75% of the patients are antibody-imaging-positive as defined above..We will enroll 6 patients (cohort 1A) at the 10mg dose level for an initial decision on feasibility. If 4 or more of these patients have 20% or more of their active lesions detectable by ^{89}Zr -DFO-MSTP2109A then we will consider the agent feasible for imaging, otherwise we will proceed to cohort 1B. If the true feasibility rate is 40%, this rule will affords more than 82% chance that cohort 1B will be opened for enrollment; this probability is less than 17% if the true feasibility is 75%. We will also require that none of these patients experience dose severe toxicity attributable to the initial 10 mg dose before cohort 1B is opened for enrollment.

If severe adverse effect (grade 3 or 4 CTCAE) is observed in any cohort we will review with MSKCC-DSMC and IRB before continuing with accrual. If 3 patients in cohort 1A do not show acceptable imaging, as described above, we will proceed to cohort 1B.

In cohort 1B, 6 more patients will be enrolled at a higher dose (20mg) for safety and pharmacokinetic evaluation. Serial blood draws will be used to estimate the pharmacokinetic profile of the 10 and 20mg ^{89}Zr -DFO-MSTP2109A in this patient population. Pharmacokinetic analysis will be performed using a non-compartmental analysis; standard parameters such as AUC, clearance, volume of distribution, and Co will be reported. Descriptive statistics will be tabulated. If 3 patients in Cohort 1B have antibody negative imaging accrual will stop. If 4 patients in cohort 1B have positive imaging we will move to cohort 2 using the best imaging dose from cohort IA or 1B..

Based on pharmacokinetic analysis from cohorts 1A and 1B an optimal time point (based visually on optimal image quality for tumor detection and clinically/logistically feasible) will be determined for imaging and cohort 2 will enroll up to 15 patients at the dose also determined from cohorts 1A or 1B. These patients will undergo a single whole-body scan at the optimal time point. The ability of ^{89}Zr -DFO-MSTP2109A to detect tumors will be estimated from this cohort using the proportion of antibody-imaging-positive patients (within +/-22% if the true detection rate is 75%).

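### Section 14.3 names only Kaplan-Meier estimates with 95% confidence intervals for relating imaging to four outcomes, but three of them are categorical as named

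*Combined protocol and SAP*

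**What the plan says.** Section 2.2 includes an exploratory aim of finding out whether "PET imaging results are related to patient outcome in patients being treated with DSTP3086S". Section 14.3 takes the outcome measures from the parent protocol 11-016 and lists them as "PSA response, RECIST response, presence or absence of new bone scan lesion and progression free survival". The whole analysis specification is then: "We will use Kaplan-Meier estimates and 95% confidence intervals to correlate these outcomes with imaging response".

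Section 14.3 does not define imaging response. Two patient-level rules appear elsewhere. Under section 14.2 a patient with a STEAP1-positive tumor "will be considered antibody-imaging-positive if 20% or more of the active lesions are detectable". Under section 9.3 "a patient will be considered positive if any of the active lesions are identified".

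Section 14.2, in explaining why the 20% threshold is low, says that "our main emphasis is to evaluate whether patients whose tumor images are positive" on the tracer are more likely to respond to the drug conjugate. Section 4.3 allows patients who "may be enrolled even if not considered for DSTP3086S therapy", so the number who contribute treatment outcomes is not fixed.

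**The concern.** Kaplan-Meier estimates the distribution of a time to an event. PSA response, RECIST response and presence or absence of a new bone lesion are categories as named. Curves or estimates by group also give no measure of association, although the sentence says they will be used to correlate outcome with imaging. The text does not say what quantity the 95% intervals describe.

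The plan therefore leaves open how three of the four comparisons will be made. An analyst could apply Kaplan-Meier literally, so that the result depends on how patients without an assessment are censored. Or the analyst could substitute another summary that the plan does not name. The undefined grouping variable adds a second open choice, because a patient can be imaging-positive under one rule and negative under the other. This relation is also the plan's stated reason for the low 20% threshold, so it should be clear how it will be estimated.

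**Working it through.** **1. Outcome against method.** Section 14.3 states no sample size, power or error rate for this objective, so there is no figure to reproduce. The check is textual.

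| Outcome in 14.3 | Type as named | Does Kaplan-Meier fit? |
|---|---|---|
| PSA response | categorical | not as named |
| RECIST response | categorical | not as named |
| New bone scan lesion, present or absent | binary | not as named |
| Progression-free survival | time to event | yes |

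**2. Is the gap filled elsewhere?** Section 2.2 gives the aim without a method. Section 3.2.4 gives the rationale only. Sensitivity and specificity in section 12 compare the antibody scan with conventional imaging, not with treatment outcome. Section 14.2 states an intention to study uptake against response, without a method. The clustering-adjusted summaries in 14.3 describe tumor uptake, not its relation to outcome. No categorical method or association measure was found.

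**3. The two positivity rules.** With one lesion detected out of n, the any-lesion rule is met. The 20% rule is met only if 1/n is at least 0.20.
- n = 5: 1/5 = 20.0%, so the rules agree.
- n = 6: 1/6 = 16.7%, so they differ.
- With two detected they first differ at n = 11: 2/11 = 18.2%.

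The documents give no distribution of lesion counts, so the number of patients affected is unknown.

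**4. What literal use of Kaplan-Meier could do to a response outcome (illustration).** The counts are assumed: 8 of 16 imaging-positive and 1 of 5 imaging-negative patients respond. Also assumed is that c non-responders leave before any response is recorded and are censored. Then 1 − KM = k/(n − c), which is the largest inflation for a given c.

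| Leavers (positive, negative) | Positive | Negative | Difference |
|---|---|---|---|
| 0, 0 | 8/16 = 50% | 1/5 = 20% | 30 points |
| 4, 2 (half of non-responders in each group) | 8/12 = 67% | 1/3 = 33% | 33 points |
| 0, 3 | 8/16 = 50% | 1/2 = 50% | 0 points |

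Under equal proportional dropout the difference hardly moves, although both rates rise. It disappears only under very unequal dropout. The illustration applies to PSA and RECIST response. It does not carry over to new bone lesions, which are an unfavorable outcome: there, counting unassessed patients as event-free would understate the rate.

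**5. How many imaging-negative patients to expect (context only).** Assume 75% positivity, the feasibility figure in 14.2 ("Antibody imaging will be considered feasible if 75% of the patients are antibody-imaging-positive"), full cohorts, and every patient on 11-016. Negatives among 6 follow Binomial(6, 0.25). P(3 or more) = 0.169, which agrees with the plan's chance of less than 17% of opening cohort 1B; P(2 or fewer) = 0.831.
- 21 patients (1A, then 2), probability 0.831: expected negatives 1.14 + 15 × 0.25 = 4.9.
- 27 patients (1A, 1B, 2), probability 0.169 × 0.831 = 0.14: expected negatives 3.25 + 1.14 + 3.75 = 8.1.
- Stop after 1B: 0.169² = 0.03.

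Here 1.14 and 3.25 are the mean negatives in a cohort of 6, given 2 or fewer and 3 or more respectively.

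**6. Precision under the proposed summaries, same assumed counts.** Clopper-Pearson 95% intervals: 1/5, 0.5% to 72%; 8/16, 25% to 75%. Risk difference 30 points, exact unconditional 95% interval about −23 to 65 points; the limits move by about a point with the way the test is inverted. Conditional odds ratio 3.76, exact 95% interval 0.28 to 221.

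**The case against.** The best defense is that this is one compressed sentence about an exploratory aim. It can be read as Kaplan-Meier for progression-free survival and estimates with confidence intervals for the rest. The outcome definitions sit in 11-016, which may define some of them as times to event; time to first new bone lesion is a natural example. Imaging response has an obvious candidate meaning in the 20% rule of the same chapter. With about 5 to 8 imaging-negative patients, no choice of method will give a firm answer.

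Part of this stands. The 11-016 point is a real limit, and the fit of the method can be judged only for the outcomes as named. Small numbers do mean that better methods will not produce narrow intervals. But the sentence applies its one method to the whole list and does not split it as the defense suggests. Section 14.3 borrows outcome measures from 11-016, not analysis methods. The 20% rule is a likely referent, but 14.3 does not say so and section 9.3 gives a different rule.

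A reader might infer more than the documents support:
- **That Kaplan-Meier will erase or distort the contrast.** The documents give no censoring rule, dropout or response counts. The illustration runs from almost no change in the difference to its disappearance, and only the extreme unequal case gives the latter.
- **That the summary will be picked after the data are seen.** A later analysis plan could fix it first.
- **That the main-emphasis wording makes this a primary analysis.** It is offered as a reason for a low threshold; sections 2.2 and 14.3 keep the aim secondary.

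**Conclusion.** The point holds as a mismatch and underspecification in a secondary analysis. The only method stated for relating imaging to outcome does not fit three of the four outcomes as named, unless 11-016 defines them as times to event. No association measure is given, the interval target is unstated, and the grouping variable has two candidate definitions that can differ from 6 active lesions upward.

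The size of any distortion cannot be derived from the documents, because the number of patients on 11-016, the response rates, the dropout and the lesion counts are all unknown. Feasibility, cohort progression, sample size and stopping are unaffected. The change should be made because it is cheap and the plan leans on this relation to justify its threshold. Confidence is medium, mainly because 11-016 could not be consulted.

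**What to change.** In section 14.3, for the patients treated on 11-016:

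- **PSA response and RECIST response:** report proportions by antibody-imaging status with exact 95% intervals, and a risk difference or odds ratio with an exact interval. Count patients without a response assessment as non-responders.
- **New bone scan lesion:** report the same summaries among patients with a follow-up scan, and show the number not assessed in each group.
- **Progression-free survival:** keep Kaplan-Meier by imaging status, with the time origin stated.
- **Grouping variable:** replace imaging response with the antibody-imaging-positive status of 14.2, and reconcile that rule with the any-lesion rule in 9.3.
- **Status:** label the analysis exploratory, with estimates and intervals only. A hazard ratio and by-cohort estimates are not needed at these numbers.
- **Link to 11-016:** if that protocol defines any of the three outcomes as a time to event, say so in 14.3.

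The cost is a few sentences in 14.3 and one reconciling edit between 9.3 and 14.2. No new data are needed: imaging status comes from the planned lesion tabulation and the outcomes from 11-016. The downside is a little more analysis, and wide intervals that will show how little the sample can settle.
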